#### **4. STUDY POPULATION**

##### **4.1. Number of participants**

We are seeking approval to recruit up to 120 participants. It is anticipated that there may be a high dropout rate of women who fail to engage with the programme or do not complete it and this information will be recorded as part of testing the efficacy of the programme. A current survey-based study has found that while women were happy to be recruited, approximately 15% fully completed all five modules of the programme and questionnaires, and 30% completed at least three of the five core modules.

#### **4.2. Inclusion/exclusion criteria**

##### **Inclusion Criteria**

- $\geq 18$  years old
- Singleton pregnancy
- Mild to moderate chronic PNMH identified with score  $\geq 2$  on PHQ-2 or GAD-2
- 16+0 – 32+6 weeks' gestation at time of recruitment.

##### **Exclusion Criteria:**

- Severe PNMH problem- schizophrenia, bipolar disorder; substance abuse/dependence, active risk of self-harm.
- Already receiving psychological therapy.
- Insufficient English language to engage with intervention or complete questionnaires.
- Unable to give informed consent.
- Illiterate
- No internet access
- Taking part in another current research project focussed on mental health.

#### **4.3. Identification of participants**

As part of the routine clinical antenatal booking appointment, all women are asked the following two questions about their mental health:

- *“During the past month have you often been bothered by feeling down, depressed hopeless?”*
- *“During the past month have you often been bothered by having little interest or pleasure in doing things?”*

Women who answer yes to one or both questions will be given summary information about the study by a member of the healthcare team. Alternatively, if a healthcare provider identifies a concern with a woman's mental health in the antenatal period prior to 32 weeks gestation, they can refer the woman to the research team. In addition to referrals from the community

setting, a research midwife will screen TRAK for potential participants attending two specialist antenatal clinics managed by our research midwives on behalf of the NHS (Obesity and preterm birth clinic). They are an essential part of the overall NHS Lothian team caring for women in pregnancy. Each hold an honorary contract with NHS Lothian and ensure they meet the standards required by the Trust to support and care for women during pregnancy. As a member of the clinical care team to whom the patient has been referred or directly in their capacity as a researcher they may approach women within the maternity setting to discuss participation in research. A research midwife will personally approach these women when they attend for their booking scan and ask if they would be interested in taking part. Alternatively, potential participants will be contacted via telephone. Interested women will be given an information sheet about the study and the researcher will answer any questions she may have. There is no pre-agreed specified time to consent. However, participants should be given time for reflection and their consent informed and voluntary. The participant also has the right to make an immediate decision to consent. If they are interested in participating and are beyond 16+0 weeks, a member of the research team will confirm eligibility using the PHQ-2 and GAD-2.

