## **2. STUDY OBJECTIVES**

### **2.1. Primary and Secondary Objectives**

Primary Objectives:

- i) Evaluate recruitment and retention to study and return of questionnaire data.
- ii) Evaluate feedback questionnaire data to assess acceptability of intervention.
- iii) Obtain an estimate of effect size for changes in anxiety, depression, social function and attachment to the developing baby.

Secondary Objectives:

[figure not shown]
- i) Measure depression (PHQ-9, EPDS, PES, WEMWS) anxiety (GAD-7) scores before and after the intervention (immediately post-intervention and 12 weeks postnatal)
- ii) Evaluate Mother-baby relationship and attachment using PAI before and after intervention and MAI at 12 weeks postnatal.
- iii) Measure pregnancy-experience pre and post intervention.
- iv) Test the ability to deliver and support the intervention, and quantify how long it typically takes women to complete the intervention.

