## **3. STUDY DESIGN**

We propose a quasi-experimental design, in which an identified population: pregnant women with mild to moderate chronic PNMH identified with score  $\geq 2$  on PHQ-2 and/or a score  $\geq 2$  on GAD -2, and who are 16-32+6 weeks' gestation will be approached by a member of the research team and encouraged to engage with intervention (cCBT programme Enjoy Your Bump). Outcomes: an assessment of recruitment, retention and return of questionnaire data. In addition, outcome data will be measured pre-intervention, immediately post-intervention and 12 weeks postnatal.

Recruitment: Pre-screening

Women will be identified for participation in this study by three different means:

1. Answering 'yes' to one or both of the routine mental health screening question at booking with their community midwife. The two routine questions asked at a booking appointment are as follows:

*"During the past month have you often been bothered by feeling down, depressed hopeless?"*

*"During the past month have you often been bothered by having little interest or pleasure in doing things?"*

Midwife will then give participant flyer about the project, and ask if they would be happy to sign a 'consent to be contacted slip' and advise them that research team may be in touch.

2. Referred to the study by a member of the healthcare team, who has identified concerns with mental health in the antenatal period (prior to 32+6 weeks of pregnancy). Only women who have signed a 'consent to be contacted' slip will be referred.
3. Self-refer to study having received a flyer about study from a member of the healthcare team.

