Answering 'yes' to one or both routine mental health screening questions at booking (approximately 8-11 weeks of pregnancy), will prompt the community midwife to give a flyer to the woman giving an overview of the study. They will ask women if they are happy to sign a 'consent to be contacted' slip. If the woman is happy to do so, the midwife will advise the woman that a member of the research team may approach them. The flyer will also contain contact information if potential participants wish to contact the research team themselves. Our research midwives manage two specialist antenatal clinics on behalf of the NHS (Obesity and preterm birth clinic). They are an essential part of the overall NHS Lothian team caring for women in pregnancy. Each hold an honorary contract with NHS Lothian and ensure they meet the standards required by the Trust to support and care for women during pregnancy. As a member of the clinical care team to whom the patient has been referred or directly in their capacity as a researcher they may approach women within the maternity setting to participate in research.

[figure not shown]
A member of the research team will personally approach these women who have consented to be contacted when they attend for their booking scan and ask if they would be interested in taking part. Alternatively, potential participants will be contacted via telephone by a member of the research team following their first scan. If potential participants are interested in participating they will be given a participant information sheet (either in person or via post).

Alternatively, women may be referred to the study by a member of the healthcare team, who has identified concerns with mental health in the antenatal period (prior to 32+6 weeks of pregnancy). In this instance, a member of the healthcare team will give a flyer giving an overview of the study to the woman, and ask if she would be willing to sign a 'consent to be contacted' slip. They would then make a referral to the research team who will then meet with the woman or contact the woman via telephone to gauge interest, answer any questions and invite for pre-screening. A patient information sheet shall be given/sent out in the post.

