Prior to invitation to attend for the first visit for this project, interested volunteers will be assessed for eligibility to take part in this study by being asked by the researcher either face to face in the antenatal clinic setting or over the telephone, the two questions in the PHQ-2 and GAD-2 questionnaires. Those who score  $\geq 2$  on either questionnaire will be eligible for

study and invited to meet the researcher for consent and first visit. The PHQ-2 and GAD-2 are short, standardised screening tools that identifies people at highest risk of depression. Those who are ineligible will be thanked for their time and given an information leaflet signposting them to appropriate perinatal mental health support. This will either be given in person, or if screening occurs over the phone this leaflet will be sent in the post.

Women will be at least 16+0 and less than 32+6 weeks pregnant when they attend to consent to this study. The meeting will take place in a clinical setting within Lothian which is most convenient for the woman to travel to. During the first visit the following process will occur:

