## Study

Consented participants will:

- i) Complete questionnaires to obtain baseline scores. They will be asked to complete:
  - a. Patient Health Questionnaire – 9( PHQ-9)
  - b. Edinburgh Postnatal Depression Score (EPDS)
  - c. Pregnancy Experience Scale (PES)
  - d. Warwick Edinburgh Mental Wellbeing Scale (WEMWS)
  - e. Prenatal Attachment Inventory (PAI)
  - f. Generalized Anxiety Disorder 7-item scale (GAD-7)
- ii) The participant will then be allocated a unique code to unlock access the EYB website. They will register to the website with the help and support of a member of the study team who will ensure the participant understands the website and can navigate to the five core 'Change Modules' which they will need to complete as part of the intervention. Each module takes the form of an online slideshow with audio. Participants work through the slides at their own pace. There is no data input required from them to complete the module. Each module has worksheets that accompany the content. Participants will be given all the worksheets at this first session. These worksheets are for participants own reference and do not need to be seen by the research team. Before leaving the session, participants will be given a leaflet signposting them to further perinatal mental health support.
- iii) The participant will have up to 38+0 weeks gestation to work through and complete the five modules and accompanying worksheets. During this time, participants will be offered ongoing support from a Research Midwife in the form of phone call and/or text message no more frequently than once weekly. We anticipate that the intervention will take about 5-8 weeks to complete.
- iv) On completion of the intervention, (up to 38+0 weeks gestation) participants will be invited to attend to repeat all measurements of assessment obtained prior to the intervention. This can be gathered either face to face or via telephone. . In addition, participants will be asked to complete an anonymous evaluation questionnaire online detailing their experience of the intervention.
- v) 12 weeks following the birth of their baby, participants will be invited to complete all questionnaires other than the PES and PAI for the final time. The MAI will be used to assess attachment. These measures shall be collected face to face or via telephone.

The volunteers will be thanked for their participation in the study. The participant data collected will be coded and anonymised.

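### Do the differing upper gestation limits for referral and consent call for a change to the plan?

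*Protocol*

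**What the plan says.** Protocol section 3 (Study Design) names the healthcare team as the second of three recruitment routes, for a team member who "has identified concerns with mental health in the antenatal period (prior to 32+6 weeks of pregnancy". The fuller description of that route later in section 3 gives the same limit. Section 4.3 (Identification of participants) describes the same route with the words "in the antenatal period prior to 32 weeks gestation, they can refer the woman to the research team".

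For consent, section 3 says that women will be "at least 16+0 and less than 32+6 weeks pregnant when they attend to consent to this study". The inclusion criterion in 4.2 starts at 16+0 and ends at "32+6 weeks' gestation at time of recruitment". The opening paragraph of section 3 also describes the population as a range ending at 32+6, so the strict inequality stands alone, even within section 3.

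At the lower end, section 4.3 says that if women are interested and "are beyond 16+0 weeks, a member of the research team will confirm eligibility using the PHQ-2 and GAD-2".

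Two other statements bear on the consequences. The first primary objective in 2.1 is "Evaluate recruitment and retention to study and return of questionnaire data". In section 3, under the heading Study, item iii says "The participant will have up to 38+0 weeks gestation to work through and complete the five modules".

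**The concern.** The protocol writes its other upper gestation limits in weeks and days, so 32 weeks in section 4.3 naturally reads as 32+0. A midwife working from 4.3 would then stop referring six days before a colleague working from section 3. A woman who consents on 32+6 meets the inclusion criterion in 4.2 but not the consent sentence in section 3.

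Recruitment is what this feasibility study sets out to measure. If the number of women referred depends on which page the referrer read, the recruitment figures could be hard to interpret. The women affected are also those with the least time before 38+0, so the boundary might seem to matter for completion of the five modules too.

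**Working it through.** The protocol gives no sample-size or power figure to reproduce here. The check sets the limits side by side in days (weeks × 7 + days).

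**Inputs**
- 16+0 = 112; 32+0 = 224; 32+5 = 229; 32+6 = 230; 38+0 = 266.
- Provider referral: last day 229 under section 3 (before 32+6); last day 223 under section 4.3 (before 32+0).
- Consent: days 112 to 229 under the consent sentence in section 3; days 112 to 230 under 4.2 and the opening of section 3.

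**Referral gap**
- 229 − 223 = 6 days, namely 32+0 to 32+5.
- The gap concerns provider referral only. Section 3 also allows self-referral after a flyer, and section 4.3 adds screening of records for two specialist antenatal clinics. Neither carries a 32-week limit, so a woman at 32+0 to 32+5 is not shut out of the study by 4.3.
- Little time remains after such a referral. From 32+0 to the last consent day is 229 − 224 = 5 days or 230 − 224 = 6 days. From 32+5 it is 0 days or 1 day. In that time she must receive the information sheet, be screened and attend a visit, so not every such referral would become an enrolment.
- The protocol gives no share of women by route and no lower limit for this referral, so a headcount cannot be derived. As an illustration only, assume that referrals are spread evenly from booking, which section 3 puts at about 8 to 11 weeks. From 8+0 (day 56) the referral window has 229 − 56 + 1 = 174 days, and 6/174 = 3.4%. From 11+0 (day 77) it has 229 − 77 + 1 = 153 days, and 6/153 = 3.9%. These are shares of referrals on this one route and are not shares of participants.

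**Consent gap**
- 230 − 229 = 1 day, out of 230 − 112 + 1 = 119 days: 1/119 = 0.8%.
- Assuming even entry and the full ceiling of 120 participants (section 4.1), 120/119 is about 1 woman.

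**Time to complete the modules**
- Consent on 32+6 leaves 266 − 230 = 36 days; consent on 32+5 leaves 266 − 229 = 37 days.
- The anticipated duration is 5 to 8 weeks, or 35 to 56 days. Both values lie just above the lower end, so the choice between them alters nothing of substance. The limit in 4.3 does not enter this comparison, because it does not set the last day for consent.

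**Lower limit**
- The phrase in 4.3 concerns screening and the one in section 3 concerns consent. In ordinary usage both mean that 16+0 has been reached. Only a very literal reading separates them, and then by one day.

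**Effect on the analysis**
- Section 8.2 plans descriptive statistics, paired t-tests of scores before and after the intervention, and thematic analysis of comments. None of these uses the gestation limit. The protocol sets no recruitment target rate or progression threshold, and names no analysis population from which a woman consented on 32+6 would be removed.

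**The case for a change.** The best case for acting is that eligibility and referral rules belong in the protocol and should be unambiguous. The referral limit is applied by clinical staff outside the research team, who cannot be expected to guess which sentence prevails. Recruitment is the first primary objective, and the remedy costs a few words with no extra patients, visits or data. Reading 32 weeks as rounding, or as deliberate lead time before consent, is conjecture, since section 4.3 says neither and section 3 gives the later limit for the same route.

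The factual part of this stands: the sentences conflict and no other text settles them. The consent point needs narrowing, because only one sentence in section 3 excludes 32+6. Section 4.2 also speaks of recruitment where section 3 speaks of consent, although the protocol defines no separate moment of recruitment.

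The argument from consequences does not stand. A six-day difference on one route, with other routes still open, cannot turn a feasible recruitment picture into an infeasible one when no threshold is set. It introduces no bias into the before-and-after comparisons.

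**Conclusion.** The inconsistency is real but clerical. It amounts to six days of provider referral and one boundary day for consent, which is about 1 woman in 120 if entry is even and the ceiling is reached. The results and their interpretation hold on every reading, so the plan needs no change.

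This conclusion rests on three features of the protocol: the 4.3 limit restricts referral and not entry, there is no recruitment threshold, and the analysis does not use the gestation boundary. If the protocol is revised for another reason, the sponsor can align the wording in sections 3, 4.2 and 4.3. Which limit is intended is for the sponsor to say, as the document does not show it.

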#### **4.4. Co-enrolment**

We do not anticipate that participants being involved in other clinical studies will affect their ability to be involved in this study, unless the other study is addressing mental health.

#### **4.5. Consent**

If a participant agrees to take part and meets eligibility by being verbally asked the questions on the PHQ-2 and GAD-2 Questionnaires, the research midwife, principal investigator, or other trained and delegated member of the research team will go through the study information with the patient and take written informed consent. Participants will have been given a patient information leaflet prior to agreeing to take part.. There is then no pre-agreed specified time to consent. However, potential participants should be given time for questions and reflection and their consent informed and voluntary. The participant also has the right to make an immediate decision to consent.

#### **4.6 Risks and Benefits to Participants**

There are few apparent risks to participating in this study. As we are looking to recruit women with mild-moderate symptoms of depression, it is important to back-up the online intervention with support from an appropriately trained individual and be able to signpost/refer women appropriately for further support. During the study, if the researcher has concerns regarding the mental wellbeing of participants beyond their scope of practice they will make the appropriate referrals in consultation with the participant. In this instance, a member of the research team will contact the woman's named midwife and/or obstetrician to discuss and make them aware of the concerns. After consultation, if thought appropriate, a referral would be made to perinatal mental health services and/or contact made with the woman's GP. Participants will be given a leaflet at the outset of the study signposting them to further mental health support.

Although there is little current evidence regarding cCBT in the pregnant population the strength of the evidence with regard to the general population suggests that participants may potentially derive some benefit from participating in this study.

#### **4.6. Participant Withdrawal**

Participants can withdraw themselves from the study at any stage without giving a reason. Participants will be made aware that withdrawing from the study will not affect their care in any way.

#### **5. SAFETY**

No safety reporting is applicable or required for this study.

#### **6. DATA COLLECTION**

Data will be collected as follows:

Demographics will be gathered from participant's health records including age, BMI, Parity, previous mental health history and postcode.

Participant's depression, anxiety and attachment scores will be collected using standardised assessment tools PHQ-9, GAD-7, PES, WEMWS, EPDS, PAI and MAI respectively. Participants will be allocated a code and their data entered onto a coded Clinical Research File.

Qualitative data will be gathered by asking participants to complete an online evaluation questionnaire following the intervention.

#### **7. STUDY OVERSIGHT**

The PI and other study investigators will provide study oversight. The Research Governance and QA office (University of Edinburgh) will review the study and determine if an independent risk assessment will be performed by an ACCORD Clinical Trials Monitor to decide (a) if monitoring is required and (b) if so, at what level. An independent risk assessment may also be carried out by the ACCORD Quality Assurance Group to determine if an audit should be performed before, during and/or after the study and if so, at what locations and at what frequency."

#### **8. STATISTICS AND DATA ANALYSIS**

## **8.2. Proposed analyses**

We will use simple descriptive statistics to describe the participant demographics.

Differences in scores from before and after the intervention will be tested using paired t-tests. Summary statistics of data obtained from the other questionnaires will be described and used as pilot data to calculate sample size for future studies.

The comments in the feedback questionnaire will be analysed using thematic analysis to identify themes within the interviews.

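### Section 8.2 fixes complete-pair t-tests as the only analysis of change although high dropout is expected; as an estimate for all enrolled women the result is biased if return depends on baseline score and change is related to baseline

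*Protocol*

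**What the plan says.** Section 8.2 of the protocol gives the analysis of change in one sentence: "Differences in scores from before and after the intervention will be tested using paired t-tests". The rest of that section covers descriptive summaries, with data "used as pilot data to calculate sample size for future studies", and thematic analysis of comments.

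Section 2.1 lists as primary objective iii: "Obtain an estimate of effect size for changes in anxiety, depression, social function and attachment to the developing baby".

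Section 4.1 sets a ceiling, not a target: "We are seeking approval to recruit up to 120 participants". It expects a "high dropout rate of women who fail to engage with the programme or do not complete it" and reports that in another, survey-based study "approximately 15% fully completed all five modules of the programme and questionnaires, and 30% completed at least three of the five core modules".

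The two follow-up assessments have different triggers (section 3, under Study). Item iv: "On completion of the intervention, (up to 38+0 weeks gestation) participants will be invited to attend to repeat all measurements". Item v is set by time since birth, with no stated condition on finishing the modules: "12 weeks following the birth of their baby, participants will be invited to complete all questionnaires other than the PES and PAI". At that visit the MAI is used for attachment.

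**The concern.** A paired t-test takes its mean change from women who have both scores; the baseline scores of all the others play no part. Where few women drop out this hardly matters. Here the protocol expects many to, and item iv ties the post-intervention score to finishing the programme, so the women who return are likely to be a selected group.

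Change usually depends on the starting score, because high scores tend to fall back and low scores to rise. If returners started lower or higher than the women enrolled, their mean change differs from the change in the whole group for that reason alone. The post-intervention and 12-week contrasts may also describe different women, and separate paired tests do nothing to link them.

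At stake is the estimate named in primary objective iii and the planning of later studies from these data.

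**Working it through.** The protocol gives no derivation for 120, so there is no calculation of the plan to reproduce.

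**Number of pairs.** Inputs from section 4.1: at most 120 women; 15% and 30% in the cited study.
- 120 x 0.15 = 18 pairs (95% binomial range 11 to 26).
- 120 x 0.30 = 36 pairs (26 to 46).
- 95% interval half-width in SDs of change, t(0.975, n-1)/sqrt(n): 0.50 with 18 pairs, 0.34 with 36, 0.18 with all 120.

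**Bias when return depends on baseline only.**

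Bias of paired change = (b - 1) x (mean baseline of returners - mean baseline of all women), where b is the slope of follow-up on baseline; b equals the correlation r when the two SDs are equal.

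Assumed, since the protocol gives none of these: SD 5 at both visits, r = 0.5, true change -2.0, 15% return, log-odds of return changing by -0.5 or +0.5 per baseline SD. Returners then lie about 0.41 SD below or above the whole group.
- Size of bias: (1 - 0.5) x 0.41 x 5 = 1.03 points.
- Slope -0.5: -2.0 + 1.03 = about -1.0. Slope +0.5: -2.0 - 1.03 = about -3.0.
- Simulated studies of 120 women gave paired changes of -1.02, -2.04 and -2.97 for slopes -0.5, 0 and +0.5. A likelihood-based repeated-measures model on the same data gave -2.04, -2.05 and -1.92, with standard error 1.2 to 1.3 against 1.2 for the paired test.
- With slope -0.5 and higher return, the paired change is about -1.4 at 50% and -1.6 at 70%.

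**Wider range.** True change -0.50 SD, correlation 0.4 to 0.7, odds ratio of return per baseline SD 0.5, 0.67 or 2:

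| Return | Paired change (SD) | Using every baseline score (SD) |
|---|---|---|
| 15% | -0.17 to -0.83 | about -0.50 |
| 30% | -0.23 to -0.77 | about -0.50 |

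The bias is zero if return is unrelated to baseline, and also zero if b = 1.

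**When return depends on the unobserved post score.** Same inputs, slope -0.5 on the post score. Returners' post scores lie 0.41 x 5 = 2.05 below the whole group, and their baselines 0.5 x 2.05 = 1.03 below.
- Paired: -2.0 - (2.05 - 1.03) = about -3.0.
- Model: -2.0 - (2.05 - 0.5 x 1.03) = about -3.5.

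If return depends on the change itself (slope -0.5 per SD of change), the paired change is about -4.1 and the model about -3.6. Both are wrong in both cases, and in the first the model is further off.

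**The case against.** Several objections limit the point.

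- A reader might infer that 15% is the plan's own retention rate, so that 85% of women will be lost. The protocol does not say so. The figure comes from another study and counts women who finished all five modules and the questionnaires; a pair needs only two scores. Since 120 is a ceiling and no rate is fixed for this study, 18 is a pessimistic scenario. It bears mainly on the post-intervention score, because of item iv.
- A reader might infer that paired tests discard the 12-week scores of women who missed the antenatal repeat. They do not: a baseline-to-12-week test keeps every woman with those two scores.
- A reader might infer bias whenever return depends on baseline severity. That needs two further conditions: change related to baseline, and all enrolled women as the target. The protocol does not state its target, and change among women who finished the programme is a coherent quantity if labelled as such.
- The model is not a cure. It creates no new follow-up scores, and it can be the worse estimate if return depends on the unobserved score. This stands as a limit, but the paired test is biased there too.
- This is a feasibility study, and missing-data detail may sit in a statistical analysis plan that is not shown. The absence of such a section is therefore no finding. What stands is that the protocol itself names a complete-pair test for an estimate it makes a primary objective, while expecting high dropout.

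**Conclusion.** The point holds in limited form and should be acted on. Certain from the document: paired t-tests are the only stated analysis of change, they use complete pairs only, and high dropout is expected.

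The size is conditional. With SD 5, r = 0.5, 15% return and a log-odds slope of 0.5 in either direction, the bias is about 1 point on a true change of -2.0, and it shrinks as return rises. None of these inputs is in the protocol. With so few pairs, chance error is also large: at r = 0.5 the SD of change is 5 x sqrt(2 x (1 - 0.5)) = 5, so the half-width with 18 pairs is 0.50 x 5 = 2.5 points. The model does not reduce that error. It removes bias that arises through observed scores, and only that.

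The document does not support saying that the paired estimate will be wrong by any given amount, or that only 18 women will contribute.

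**What to change.** Amend section 8.2 as follows.
- Make the main estimate a likelihood-based repeated-measures model per scale, with visit as a categorical factor, unstructured within-woman covariance and every woman with a baseline score included.
- Use baseline, post-intervention and 12 weeks for PHQ-9, EPDS, GAD-7 and WEMWS; baseline and post-intervention only for PES and PAI, which are not collected at 12 weeks. Describe the MAI only, since it has no baseline.
- Compare baseline scores and demographics of women with and without each follow-up.
- Keep the paired change as a sensitivity analysis labelled completers-only.
- State with the result that the model assumes missingness is explained by observed scores, and that if return depends on the unobserved post score or on response both estimates are biased and the model may be further off.

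The cost is about one paragraph and a little analysis time, with no new data or visits. The interval may be slightly wider than that of the paired test.
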